4.1. Overall Design

This is a single-centre, randomised, double-blind, placebo-controlled, proof-of-concept Phase 2 study in healthy adult male or female participants aged between 18 and 55 years old, inclusive, utilising:

- Investigational medicinal product (IMP) (active): Neumifil, [REDACTED] once daily for 3 days on Days -3 to -1 (multiple dose active treatment) or [REDACTED] single dose on Day -3 (single dose active treatment), intranasally administered ([REDACTED] Neumifil [REDACTED])
- IMP (placebo): Matching placebo, once daily for 3 days on Days -3 to -1 (placebo treatment) or once daily for 2 days on Days -2 and -1 (single dose active treatment), intranasally administered [REDACTED]
- Challenge agent: influenza A/Perth/16/2009 (H3N2) virus challenge strain, $\sim 10^{5.5}$ tissue culture infective dose (50%) (TCID₅₀), intranasally administered.

The primary goal of this Phase 2 study is to assess the pre-exposure prophylactic antiviral activity against influenza, safety, and tolerability of Neumifil via a human viral challenge model.

Each participant will receive one of 3 treatments:

- Neumifil once daily for 3 days on Days -3 to -1 (multiple dose active treatment).
- A single dose of Neumifil on Day -3 and placebo once daily on Days -2 and -1 (single dose active treatment).
- Placebo once daily for 3 days on Days -3 to -1.

A total of up to evaluable 100 participants is planned to be enrolled in this study: 30 participants on multiple dose active treatment, 30 participants on single dose active treatment, and 40 participants on placebo.

The expected duration of study participation for a participant is 4 months, with the following sequence and duration of study phases:

- **Screening phase:** From Day -93 to Day -5 (prior to quarantine admission). Historical generic screening data collected through the hVIVO generic screening process may be transferred to this study after the study-specific consent form has been signed by the participant.
- **Inpatient phase:** Participants will be resident in the quarantine unit for approximately 13 days (from Day -4 to Day 8). Procedures will include:
 - **Pre-human viral challenge:**
 - Admission to quarantine unit on Day -4.
 - Baseline assessments and randomisation will be conducted as per Schedule of Events (SoE) up to Day -3, predose.
 - Administration of Neumifil and/or placebo once daily on Days -3 to -1, according to randomisation.
 - **Human viral challenge:**
 - Influenza virus inoculation on Day 0.

- **Post-human viral challenge:**
 - Day 1 onwards and each day – study assessments will be conducted as per SoE.
 - Discharge from the quarantine unit on Day 8 [REDACTED]
[REDACTED]
[REDACTED]
- **Outpatient phase:**
 - Final follow-up visit: Day 28 (±3 days).

Study assessments will be conducted as per SoE

The Study Schematic, showing participant progression through the study, is presented in [Section 1.1](#), Study Schematic: On-study Participant Progression. The SoE is presented in [Section 1.2](#), Schedule of Events.

4.2. Scientific Rationale for Study Design

The study will be conducted by hVIVO Services Limited, which has extensive experience with influenza challenge studies. Numerous studies have been performed using experimental influenza infection in human participants. To date, in hVIVO's studies, over 400 participants have been successfully and safely inoculated with influenza A/Perth/16/2009 (H3N2) virus. These studies demonstrated that adults could be infected by nasal inoculation and that experimental infection was safe. This influenza strain has been shown to cause symptoms and virus shedding that closely match natural infection.

Administration of IMP and challenge with influenza A/Perth/16/2009 (H3N2) virus will take place in hVIVO's specialised clinical facilities, in a quarantine unit. Standard study procedures (including collection of blood, urine, and nasopharyngeal secretions for assessment of safety and efficacy) have been employed in previous studies conducted by hVIVO.

Blinding, Control, and Randomisation

The placebo control will be used to establish the frequency and magnitude of changes in endpoints that may occur in the absence of active treatment. It will allow a comparative evaluation of the efficacy of Neumifil.

Blinding will prevent the occurrence of conscious and unconscious bias in the conduct and interpretation of the study.

Randomisation will be used to prevent bias in the assignment of participants to treatment arms, to increase the likelihood that known and unknown participant characteristics (e.g., demographic and baseline characteristics) are equally balanced across treatment arms, and to enhance the validity of statistical comparisons across treatment arms.

4.3. Justification for Dose

All doses administered in the first-in-human study were well tolerated. In the multiple dose part of the study Neumifil was administered as a single daily dose of [REDACTED] [REDACTED]. Based on the safety profile and tolerability of Neumifil seen to date 3 [REDACTED] [REDACTED] [REDACTED] would be appropriate.

An inoculum titre of approximately $10^{5.5}$ TCID₅₀ of the influenza A/Perth/16/2009 (H3N2) virus strain has been shown to cause disease profiles that are consistent with the mild to moderate disease profiles expected with wild-type challenge viruses in healthy adult participants.

4.4. Population to be Studied

Healthy adult participants.

4.5. Rationale for Trial Endpoints

The measures for evaluation of the safety and tolerability profile of Neumifil are standard for most clinical studies and follow the recommendations in the International Council for Harmonisation (ICH) guidelines.

The measures for evaluation of the pre-exposure prophylactic antiviral activity of Neumifil against influenza have been employed in previous studies conducted by hVIVO and are appropriate to characterise the efficacy of Neumifil, considering the Neumifil mode of action.

Biomarkers (cytokine and chemokine) and ADAs are exploratory in nature and do not have predefined endpoints.

4.6. End of Study Definition

A participant is considered to have completed the study if he/she has completed all phases of the study including the last scheduled study visit or the last unscheduled study visit, as applicable. If a safety visit is required after the last scheduled study visit, this will be at the discretion of the PI/investigator as a duty of care, e.g., repeat spirometry or laboratory tests. These discretionary follow-up visits will not be considered part of the study data unless they represent follow-up and closure on an AE or SAE identified during the study period.

The end of the study is defined as the date of the last visit of the last participant in the study.

5. Study Population

Prospective approval of protocol deviations to recruitment and enrolment criteria, also known as protocol waivers or exemptions, is not permitted.

5.1. Inclusion Criteria

No.	hVIVO APPROVED STANDARD INCLUSION CRITERIA (Viral Challenge Volunteer Studies) Final v11.0, 08FEB2022
To be eligible for the study, participants must meet all the following inclusion criteria:	
1.	Written informed consent signed and dated by the participant and the investigator obtained before any assessment is performed.
2.	Adult male or female aged between 18 and 55 years old, inclusive, on the day prior to signing the consent form.
3.	A total body weight ≥ 50 kg and body mass index (BMI) ≥ 18 kg/m ² and ≤ 35 kg/m ² .
4.	In good health with no history, or current evidence, of clinically significant medical conditions, [REDACTED].
5.	Participants will have a documented medical history either prior to entering the study or following medical history review with the study physician at screening.
6.	The following criteria are applicable to female participants participating in the study. 
 a) Females of childbearing potential must have a negative pregnancy test prior to enrolment. b) Females of non-childbearing potential: 
 a. Postmenopausal females defined [REDACTED] b. Documented status as being surgically sterile [REDACTED]
7.	The following criteria apply to female and male participants: 
 a) Female participants of childbearing potential must use 1 form of highly effective contraception. [REDACTED]

NO	hVIVO APPROVED STANDARD EXCLUSION CRITERIA (Viral Challenge Volunteer Studies) Final v11.0, 08FEB2022
4.	Females who: 
 a) Are breastfeeding, or b) Have been pregnant ██████████ r c) Have a positive pregnancy test at any point during screening or prior to first dosing with IMP.
5.	
 a) Any history of anaphylaxis or history of severe allergic reactions ██████████
6.	Venous access deemed inadequate ██████████
7.	
 a) Any significant abnormality altering the anatomy of the nose in a substantial way or nasopharynx that may interfere with the aims of the study and, in particular, any of the nasal assessments or viral challenge. b) History of nasal polyps c) Nasal inflammation present at screening on Day -4 d) Any clinically significant history of epistaxis (large nosebleeds) within the last 3 months of the first study visit and/or history of being hospitalised due to epistaxis on any previous occasion. e) Any nasal or sinus surgery within 3 months of the first study visit.
Prior or Concomitant Medications and Assessments	
8.	
 a) Evidence of vaccinations within the 4 weeks prior to the planned date of first dosing with IMP. b) Intention to receive any vaccination(s) before the last day of follow-up (with the exception of vaccinations recommended for COVID19 as defined by Medicines and Healthcare Regulatory Agency (MHRA)/government vaccination guidelines). No travel restrictions apply after the Day 28 (±3 days) follow-up visit. c) Receipt of influenza vaccine (or another IMP relating to treatment of influenza) in the last 6 months prior to the planned date of viral challenge OR a diagnosis of influenza or influenza-like illness confirmed by a physician within the last 2 months prior to screening.
9.	Receipt of blood or blood products, or loss (including blood donations) of 550 mL or more of blood during the 3 months prior to the planned date of first dosing with IMP or planned during the 3 months after the final follow-up visit.
10.	
 a) Receipt of any investigational drug within 3 months (or 5 half-lives of the IMP used in the other study, whichever is greater), prior to the planned date of first dosing with IMP. b) Receipt of 3 or more investigational drugs within the previous 12 months prior to the planned date of first dosing with IMP.

NO	hVIVO APPROVED STANDARD EXCLUSION CRITERIA (Viral Challenge Volunteer Studies) Final v11.0, 08FEB2022
Other	
16.	Those employed or immediate relatives of those employed at hVIVO or the sponsor.
17.	Any other finding that, in the opinion of the investigator, deems the participant unsuitable for the study.

5.3. Lifestyle Considerations

5.3.1. Meals and Dietary Restrictions

[REDACTED]

[REDACTED]

[REDACTED]

[REDACTED]

5.3.2. Caffeine, Alcohol, and Tobacco

[REDACTED]

[REDACTED]

[REDACTED]

[REDACTED]

[REDACTED]

[REDACTED]

[REDACTED]

[REDACTED]

5.3.3. Activity

Participants must refrain from strenuous exercise [REDACTED]

[REDACTED]

[REDACTED]

[REDACTED]

5.3.4. Other Restrictions

Participants will be instructed to avoid close contact with vulnerable people as described in [Section 2.3.1.1](#), Vulnerable Population, for 2 weeks after they leave the quarantine unit.

5.4. Screen Failures

[REDACTED]

[REDACTED]

[REDACTED]

[REDACTED]

[REDACTED]

[REDACTED]

[REDACTED]

[REDACTED]

6. Study Intervention

Study intervention is defined as any investigational intervention(s), marketed product(s), placebo, or medical device(s) intended to be administered to a study participant according to the study protocol.

Study interventions administered to participants are described in [Table 6-1](#).

6.1. Study Intervention(s) Administered

Table 6-1: Study Interventions

Intervention Name	Neumifil	Placebo	Influenza A/Perth/16/2009 (H3N2) Virus
Type	Drug	Other	Virus
Dose Formulation	Liquid for intranasal spray administration	Liquid for intranasal spray administration	Capped vial, liquid for intranasal drops administration
Unit Dose Strength(s)	██████████	Not applicable	The challenge agent titre is determined in an infectivity assay. The dose is approximately $10^{5.5}$ TCID ₅₀
Dosage Level(s)	Multiple dose active treatment:		A single dose of challenge agent will be delivered
	3-day once daily dosing regimen of ██████████ ██████████ (Days -3 to -1), divided between left and right nostrils ██████████ ██████████	Not applicable	
	Single dose active treatment:		
	██████████ (Day -3) divided between left and right nostrils ██████████ ██████████	2-day once daily dosing regimen of 0.28 mL (Days -2 and -1), divided between left and right nostrils ██████████ ██████████	
Placebo treatment:			

	Not applicable	3-day once daily dosing regimen ██████████ (Days -3 to -1), ██████████ ██████████ ██████████ ██████████ ██████████	
Route of Administration	Intranasal	Intranasal	Intranasal
Use	Experimental	Placebo	Infectious challenge agent
Sourcing	Provided by Pneumagen	Provided by Pneumagen	Provided centrally by hVIVO
Packaging and Labelling	The details of the packaging and labelling will be provided in the study-specific pharmacy manual	The details of the packaging and labelling will be provided in the study-specific pharmacy manual	Influenza challenge agent will be provided in vials. The details of the challenge agent provision will be provided in the analytical plan (AP)
Current/Former Name(s) or Alias(es)	Not applicable	Not applicable	Not applicable

6.2. Preparation/Handling/Storage/Accountability

6.2.1. Investigational Product

Neumifil and placebo (IMP) will be supplied in prefilled nasal spray pump devices for intranasal administration. Details on dose preparation and administration are provided in the study-specific pharmacy manual.

hVIVO will receive supplies of IMP after the supply has received qualified person sign off by the Good Manufacturing Practice (GMP) sponsor's representative/pharmacy provider and has been released for shipment. All IMP supplies will be used only for this protocol and for no other purpose.

Ready-to-dispense IMP will be supplied at the beginning of the study. Once received at hVIVO, hVIVO study staff will perform stock level accountability and the IMP will be stored securely, according to the directions on the IMP labels. IMP accountability will be controlled by hVIVO and monitored by the study monitor throughout the study and at study close-out.

The PI/investigator will ensure that all supplies are received by a responsible person, all deliveries and returns are documented and signed for, and the condition of the IMP is monitored. Accurate records will be

kept of when and how much IMP is dispensed and used in the study. Any reasons for departure from the protocol dispensing regimen will be recorded.

Accountability records will be available for verification by the study monitor at each monitoring visit. At the completion of the study, there will be a final reconciliation of all IMP.

6.2.2. Challenge Agent

The challenge agent used in this study is influenza A/Perth/16/2009 (H3N2) virus.

The challenge agent stock was manufactured under current good manufacturing practices (cGMP). The challenge agent stock has undergone quality testing performed during manufacturing (identity, appearance, sterility, infectivity, and contaminants) according to pre-determined specifications, and has subsequently also passed an extensive panel of adventitious agent testing. The challenge agent is stored in a secure -80°C freezer (normal temperature range -60°C to -90°C).

Each participant will be allocated a unique vial containing the challenge agent and will receive the inoculum intranasally. The inoculum will be prepared and/or provided according to the hVIVO Analytical Plan (AP) and administered in accordance with hVIVO standard operating procedure (SOPs).

All administrations will be made by a member of the study staff and witnessed by a second study staff member. The exact time of challenge agent inoculation will be recorded in the administration log. Accurate records will be kept of when and how much inoculum is prepared and/or provided and used. The oversight process will be signed off prior to administration of the challenge agent. Any noncompliance or problems with the inoculation will be recorded in the participant's source notes and reported to the PI/investigator.

[REDACTED]

6.2.3. All Study Interventions

The PI/investigator or designee must confirm appropriate temperature conditions have been maintained during transit for all study intervention received and that any discrepancies are reported and resolved before use of the study intervention.

Only participants enrolled in the study may receive study intervention and only authorised investigator site staff may supply or administer study intervention. All study intervention must be stored in a secure, environmentally controlled area, and monitored (manual or automated) in accordance with the labelled storage conditions with access limited to the PI/investigator and authorised investigator site staff.

The PI/investigator, institution, or the head of the medical institution (where applicable) is responsible for study intervention accountability, reconciliation, and record maintenance (i.e., receipt, reconciliation, and final disposition records)

Further guidance and information for the final disposition of unused study interventions are provided in the pharmacy manual.

6.3. Randomisation and Blinding

[REDACTED]
[REDACTED]
[REDACTED]
[REDACTED] The randomisation number encodes the participant's assignment to one of 3 study arms (Neumifil multiple dose active treatment, Neumifil single dose active treatment, or placebo) in a 3:3:4 ratio.

Randomisation numbers will be assigned sequentially in ascending order; and once assigned, that randomisation number shall not be reassigned. The study site will keep a log of the randomisation number assigned to each participant.

A designated unblinded statistician, separate from the conduct or analysis of the study, will be responsible for the computer-generated randomisation schedule. Sealed copies of the randomisation code will be stored in a secure location.

Randomisation numbers will follow a 3-digit format e.g., [001]. If participants are replaced as per [Section 7.4](#), Participant Replacement Strategy, the replacement participant will be assigned a new, unique randomisation number equalling the randomisation number of the replaced participant, plus 100. This will ensure that the replacement participant receives the same allocated, blinded treatment as the participant who is being replaced.

A copy of the randomisation code list will be sent to the unblinded pharmacist preparing the IMP, so that IMP (Neumifil/placebo) can be prepared for each participant as appropriate. An independent statistician prepares the randomisation schedule, and the GMP pharmacy provider's pharmacist/designee will prepare the participant level IMP doses in line with the randomisation schedule.

Each participant will be dispensed blinded IMP (Neumifil/placebo), labelled with his/her unique randomisation number, throughout the study. With the exception of the unblinded pharmacist, the unblinded statistician preparing the randomisation code list, and the quality assurance auditors where necessary, the PI/investigator and all other clinical and nonclinical staff, (including the study statistician, data management staff), and the participants will remain blinded to the treatment allocation until after the database has been locked and approval for study unblinding has been given.

Following database lock, on receipt of authorisation from the sponsor, a copy of the randomisation code list will be provided to the study statistician to conduct study unblinding prior to analysis.

Individual access to a secured Interactive Web Response System (IWRS) will be provided to the investigator. The website, compliant with 21CFR part 11 guidelines, will be used if unblinding is necessary. In case of an emergency, the investigator has the sole responsibility for determining if unblinding of a participant's intervention assignment is warranted. The blind should only be broken where knowledge of the IMP received is required to provide appropriate patient care. Participant safety must always be the first consideration in making such a determination. If the investigator decides that unblinding is warranted, the investigator should make every effort to contact the sponsor prior to unblinding a participant's intervention assignment unless this could delay emergency treatment of the participant. When the investigator breaks the code, he/she will have to indicate on the web site the reason of unblinding. The person who performed the unblinding and the date of time of code breaking will be automatically recorded. After confirmation the nature of treatment will appear on the screen. A notification with the nature of treatment will also be provided

by email. A notification, without the nature of treatment, will be provided to the study team. The investigator must notify the sponsor within 24 hours that the code has been broken.

Even if the code is broken, blood samples for safety, efficacy, and other assessments will continue to be drawn for the remainder of the planned study period following the last dose if doing so will not compromise participant welfare.

Dosing with IMP must be discontinued after unblinding, but the participant will be followed up until resolution of any AEs.

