7.6. Features

This study is designed to be able to utilise features to enhance study safety, efficiency, and efficacy. These design elements are predefined in their scope and limit, as detailed in [Table 7-2](#).

The implementation of study-specific features will be documented in a non-substantial amendment. Generic features may be implemented at any time at the discretion of the PI/investigator.

Table 7-2: Features

Design Category	Feature	Limit
Generic		
Cohort(s)	
 Participants who have been withdrawn (for any reason) may be replaced (sponsor and/or PI/investigator discretion). Participants who are replacing a withdrawn participant may be randomised for inclusion, and dosed/challenged: 
 In an ongoing cohort In a new cohort Separately. Any study cohort may run at the same time The number of participants enrolled in each cohort may be reduced or increased (sponsor and/or PI/investigator discretion) to best meet the study objectives. 	
 The stopping rules of the study must be always adhered to, and replacement participants may not be enrolled to replace participants who have been withdrawn from the trial due to the meeting of stopping rules. The total number of study participants will not exceed 100 evaluable participants. Replacement participants will be given replacement randomisation numbers (see Section 7.4, Participant Replacement Strategy). All protocol-defined rules and safety criteria must be met before any participant commences the study.
Sample/Specimen	
 The PI/investigator may perform additional safety assessments, at any time, if they believe them to be clinically required. Where clinically required (sponsor and/or PI/investigator discretion), participants may be referred for consultation(s) and/or investigation(s) under the care of a specialist physician. 	
 The maximum blood volume will not be exceeded. Any required additional safety assessments, or specialist referrals, will be conducted on a case-by-case basis. As such the maximum number needed cannot be prospectively defined.

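### The plus-100 replacement rule has no visible exception for a broken code, so an investigator who has seen the replaced participant's treatment would know the replacement's

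*Combined protocol and SAP*

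**What the plan says.** Protocol Section 6.3 gives a replacement a number "equalling the randomisation number of the replaced participant, plus 100", and states the purpose: "This will ensure that the replacement participant receives the same allocated, blinded treatment as the participant who is being replaced". The replacement is therefore not randomised afresh; the arm is carried over.

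The site can see the numbers: "The study site will keep a log of the randomisation number assigned to each participant", and each participant's IMP is "labelled with his/her unique randomisation number".

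On emergency code breaks, the same section begins: "In case of an emergency, the investigator has the sole responsibility for determining if unblinding" is justified. The code is broken through the web system, and "After confirmation the nature of treatment will appear on the screen". An email also carries the treatment, while the study team's notice omits it. Then "Dosing with IMP must be discontinued after unblinding", although follow-up continues.

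On who may be replaced, Section 7.6, Table 7-2 says: "Participants who have been withdrawn (for any reason) may be replaced (sponsor and/or PI/investigator discretion". The one exclusion visible there is for withdrawals that result from meeting the stopping rules. Section 7.4, on replacement strategy, shows a single sentence; the rest is redacted.

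Section 6.3 also says that, apart from the unblinded pharmacist, the unblinded statistician and (where necessary) auditors, everyone including the investigator stays blinded until after database lock.

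**The concern.** Emergency unblinding is an accepted exception to the blind for the participant concerned. It should not also reveal the allocation of someone not yet enrolled. Under the plus-100 rule it would: the investigator who broke the code for 023 would know what 123 is to receive, because the rule is printed in the protocol and the numbers are visible at the site.

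At stake is allocation concealment for that replacement. Someone who knows the arm could be influenced in deciding whether to replace at all, in choosing whom to enrol, and in later judgements on that participant such as the causal attribution of adverse events. Section 4.2 relies on randomisation and blinding to prevent these influences.

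**Working it through.** The plan states no figure for this point, so there is none to reproduce. The check is a trace through the text, followed by simple arithmetic on size.

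**Trace**

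1. *Code break.* The investigator decides and sees the treatment (Section 6.3).
2. *Effect on that participant.* Dosing stops. If the break comes before the third dose, the planned dose has not been received, so the participant cannot meet the per-protocol definition (Section 9.3). That is the set for the primary analysis (Section 9.4.4). With up to 100 evaluable participants planned (Section 4.1), there is then a reason to want a replacement.
3. *Withdrawal and replacement.* Discontinuing dosing is not the same as withdrawal. If the participant is also withdrawn, Table 7-2 permits replacement, with the decision resting with the sponsor and/or investigator. The stopping rules in Table 7-1 concern SUSARs, a collective safety pattern attributed to IMP, and unexpected virus-related events. An emergency code break need not meet any of these.
4. *Number and arm of the replacement.* The number is n + 100 and the arm is that of n (Section 6.3).
5. *Who enrols and doses.* The investigator or a designee administers the study intervention (Section 6.4).

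Steps 1 and 4 together contradict Section 6.3's description of the replacement's treatment as blinded, and its statement that the investigator remains blinded until after lock.

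**Is the link unique?** Taking the original numbers as 001 to 100, replacements are 101 to 200. No number occurs in both ranges, and each replacement number points to exactly one original.

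**What knowledge is gained?** Under 3:3:4 allocation the arm probabilities are 0.30, 0.30 and 0.40.

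| Knowledge | Arm guessed correctly (best guess) | Active v placebo guessed correctly (best guess) |
|---|---|---|
| Blind | 0.40 | 0.30 + 0.30 = 0.60 |
| After a code break on n, screen names the arm | 1.00 | 1.00 |
| After a code break on n, screen shows only active or placebo | 1.00 if placebo; 0.50 if active (3:3) | 1.00 |

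The protocol does not define what the screen shows; I assume at least active or placebo.

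**Size.** The primary comparison is 60 pooled active against 40 placebo (Section 9.2).

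- One such replacement: 1/60 = 1.7% of pooled active, or 1/40 = 2.5% of placebo.
- The documents give no rate of code breaks. Assuming 0 to 3 such replacements among 100 evaluable participants: 0% to 3% of the data. If all 3 fell on one side of the primary comparison, that would be 3/60 = 5.0% of pooled active or 3/40 = 7.5% of placebo.

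**The case against.** The strongest objection is that the replacement rules cannot be fully read. Section 6.3 applies plus-100 to replacements made under Section 7.4, and most of Section 7.4 is redacted, as are the opening of Section 6.3 and the discontinuation criteria in Section 7.2. An exclusion for unblinded participants could be stated there. This stands: the point has to be put as something to confirm or add, not as a proven omission.

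Second, the chain is long. It needs an emergency code break in a healthy volunteer, then withdrawal, then a discretionary decision to replace. Some of the likeliest cases fall under the stopping rules and cannot be replaced. There are only three dosing days, so a code break after Day -1 costs no dose and may prompt no replacement. This also stands, and it limits how often the problem can arise. It does not remove it.

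Third, disclosure is contained, since the study team's notice omits the treatment. That protects other staff, but not against knowledge held by the investigator who broke the code and who may decide on the replacement.

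A reader might infer two stronger things. One is that every replacement's allocation leaks, because staff could guess the arm of someone who withdrew with a nasal or taste reaction. The documents do not support this: the reactions listed in Section 2.1.2.2 and Table 2-1 are mostly nasal and taste effects, and Table 2-1 says that placebo excipients may also cause effects. The other is that the primary endpoints would be biased. They rest on RT-PCR and on diaries completed by the participant (Sections 3 and 8.3.2), and nothing in the chain unblinds the replacement participant. Nor does the investigator alone settle per-protocol membership; that is done at a data review meeting before lock (Sections 9.3 and 9.4.3.2).

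**Conclusion.** The concern holds in a narrow form. On the visible text, a replacement for a participant whose code was broken would have an allocation known to the investigator before enrolment, contrary to Section 6.3's own statements. It rests on three assumptions: that the redacted text contains no safeguard, that the displayed treatment identifies at least active or placebo, and that the same investigator is involved in replacing, enrolling or assessing.

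The expected effect is small. A reader might size it against a single 30-participant active arm (1/30 = 3.3%), but the comparisons of individual arms with placebo are exploratory, so the pooled denominators apply. Few events are expected: 60 × 0.278 × 0.30 = 5.0 symptomatic infections in pooled active and 40 × 0.278 = 11.1 in placebo. That does not make one known allocation decisive, since knowing the arm does not change a PCR result or a self-scored diary. This is a gap in allocation concealment that is cheap to close, not a threat to the primary result.

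**What to change.** First confirm whether the redacted part of Section 7.4 already covers this. If it does not, add to Sections 6.3 and 7.4 that a participant whose code has been broken is not replaced under the plus-100 rule, and that any replacement takes the next unused number on the concealed schedule. If no unused number remains, a short reserve list can be generated in advance by the unblinded statistician and kept concealed. List any such cases in the clinical study report.

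Keep plus-100 for all other replacements. It preserves the planned 30:30:40, and the case for abandoning it generally has not been made.

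The cost is a sentence or two of protocol text, possibly a few extra labelled IMP kits, and a possible departure of one or two participants from 30:30:40. Table 7-2 already allows cohort sizes to vary.
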